8.5.2. Secondary Analyses

The proportion of participants with HIV-1 RNA < 50 copies/mL at Weeks 28, 38, and 80, respectively, will be analyzed using the same methods as for the primary efficacy endpoint.

The changes from baseline in \log_{10} HIV-1 RNA and CD4+ cell count will be summarized using descriptive statistics. The differences in changes from baseline in \log_{10} HIV-1 RNA and CD4+ cell count between treatment groups and the associated 95% CIs will be constructed using analysis of variance (ANOVA) models adjusting for the baseline HIV-1 RNA level.

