1.2. Study Design

Design Configuration and Subject Population

This is a Phase 2, randomized, open label, active controlled, multicenter study.

Approximately 175 treatment-naive PWH who meet all eligibility criteria will be randomized in a 2:2:2:1 ratio to 1 of the following 4 treatment groups. Randomization will be stratified by HIV-1 RNA level ($\leq 100,000$ copies/mL or $> 100,000$ copies/mL) at screening.

Treatment Groups

Treatment Group 1 (n = 50)

Induction: Subjects will receive oral LEN 600 mg, 600 mg, and 300 mg, without regard to food, at Days 1, 2, and 8 respectively. Subjects will also begin oral daily emtricitabine (F)/TAF (200/25 mg), without regard to food from Day 1 onwards for a total of 28 weeks. On Day 15 subjects will receive subcutaneous (SC) LEN 927 mg, without regard to food.

Maintenance: Subjects will receive SC LEN 927 mg at Week 28 and every 26 weeks thereafter. Subjects will discontinue oral daily F/TAF (200/25 mg) at Week 28 and begin taking oral daily TAF (25 mg), without regard to food.

Treatment Group 2 (n = 50)

Induction: Subjects will receive oral LEN 600 mg, 600 mg, and 300 mg, without regard to food at Days 1, 2, and 8 respectively. Subjects will also begin oral daily F/TAF (200/25 mg), without regard to food from Day 1 onward for a total of 28 weeks. On Day 15 subjects will receive SC LEN 927 mg, without regard to food.

Maintenance: Subjects will receive SC LEN 927 mg at Week 28 and every 26 weeks thereafter. Subjects will discontinue oral daily F/TAF (200/25 mg) at Week 28 and begin oral daily BIC (75 mg) without regard to food.

Treatment Group 3 (n = 50)

Subjects will receive oral LEN 600 mg and 600 mg without regard to food at Days 1 and 2, respectively. On Day 3, subjects will begin oral daily LEN 50 mg, without regards to food. Subjects will begin oral daily F/TAF (200/25 mg), without regard to food from Day 1 onwards.

Treatment Group 4 (n = 25)

Subjects will receive oral daily bictegravir/emtricitabine/TAF (B/F/TAF, 50/200/25 mg), without regard to food at Day 1 and throughout their participation in the study.

Key Eligibility Criteria

Treatment naive PWH who meet the following criteria:

- Age \geq 18 years of age at Screening
- Plasma HIV-1 RNA \geq 200 copies/mL at Screening
- CD4+ cell count \geq 200 cells/ μ L at Screening

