1.3. Sample Size and Power

A sample size of 50 subjects in Treatment Groups 1 to 3, respectively, was chosen to estimate the response rate of HIV-1 RNA < 50 copies/mL at Week 54. A total sample size of 75 subjects for each pair of comparisons (ie, between each of the LEN-containing regimen groups [Treatment Groups 1 to 3, n = 50] and the B/F/TAF [Treatment group 4, n = 25]) will provide 39% power to evaluate non-inferiority with respect to the response rate of HIV-1 RNA < 50 copies/mL at Week 54. In this sample size and power calculation, it is assumed a response rate is 90.9% (based on pooled data from Studies GS-US-380-1489 and GS-US-380-1490) for each treatment group and a non-inferiority margin is 0.12.

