3.3. Strata and Covariates

Randomization was stratified by HIV-1 RNA level ($\leq 100,000$ copies/mL or $> 100,000$ copies/mL) at screening.

Efficacy analyses will include HIV-1 RNA stratum ($\leq 100,000$ vs. $> 100,000$ copies/mL) at baseline as a stratification factor. The HIV-1 RNA stratum will be reclassified using baseline HIV-1 RNA level for analysis purposes.

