3.8. Analysis Visit Windows

3.8.1. Definition of Key Dates and Study Day

Study Day 1 is defined as the day when the first dose of study drug was taken, as recorded on the Study Drug Administration eCRF. For subjects in Treatment Groups 1-3, the earliest of the first dose dates of any component (ie, LEN or F/TAF) is considered as the first dose date of the study drug.

Last Dose Date is defined as follows for subjects who prematurely discontinued study drug according to Study Drug Completion eCRF.

- For subjects who receive SC injection, the last dose date is defined as the latest nonmissing end date of the study drug used with LEN.
- For subjects who do not receive SC injection, the last dose date is defined as the earliest of the last dose date of any study drug.
- If the date of last dose is incomplete or missing (eg, due to lost to follow-up), the latest nonmissing study drug start dates and end dates, the clinic visit dates, and the laboratory visit dates excluding the dates of any follow-up visits will be used to impute the last dose date.

Study Days are calculated relative to Study Day 1 of study drug and derived as follows:

- For postdose study days: Assessment Date – First Dose Date + 1
- For days prior to the first dose: Assessment Date – First Dose Date

Baseline Value is defined as the last value obtained on or prior to the first dose of study drug.

Last Study Date is the latest nonmissing clinic visit dates, and/or the laboratory visit dates, and/or latest AE onset date and end date, whichever is latest, including the any follow-up visit dates, for subjects who prematurely discontinued study according to the Study Completion eCRF.

Last Exposure Date is defined as follows for subjects who prematurely discontinued study drug according to Study Drug Completion eCRF. This date is defined considering the prolonged exposure of LEN after the last dose date of LEN.

- Treatment Groups 1 and 2:
 - For subjects who receive SC injection, last exposure date is defined as last study date.
 - For subjects who do not receive SC injection, last exposure date is defined as the minimum of the last dose date plus 60 days and the last study date.

- Treatment Group 3: last exposure date is defined as the minimum of the last dose date plus 60 days and the last study date.
- Treatment Group 4: last exposure date is defined as the minimum of the last dose date plus 30 days and the last study date.

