5.2. Other Baseline Characteristics

The following baseline disease characteristics will be summarized by treatment group and overall using descriptive statistics for continuous variables and using number and percentage of subjects for categorical variables:

- HIV-1 RNA (log₁₀ copies/mL)
- HIV-1 RNA categories (copies/mL): (a) ≤ 100,000, (b) > 100,000
- CD4 cell counts (/uL)
- CD4 cell counts categories (/uL): (a) < 50, (b) ≥ 50 to < 200, (c) ≥ 200 to < 350, (d) ≥ 350 to < 500, and (e) ≥ 500
- CD4 percentage (%)

The summary of these baseline disease characteristics will be provided for the Safety Analysis Set. Statistical comparison across treatment groups will be conducted similarly as described for the demographic and baseline characteristics.

A by-subject listing of other baseline characteristics will be provided by subject ID number in ascending order.

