6.2.1. Analysis of the Secondary Efficacy Endpoints

The change from baseline in \log_{10} HIV-1 RNA and in CD4+ cell counts will be based on the FAS and summarized up to the visits with available data using descriptive statistics. The differences in changes from baseline in \log_{10} HIV-1 RNA and CD4+ cell count between each of the LEN-containing treatment groups (Treatment Groups 1-3) and the B/F/TAF group (Treatment Group 4) and the associated p-values and 95% CIs will be constructed using analysis of variance (ANOVA) models adjusting for the baseline HIV-1 RNA level ($\leq 100,000$ copies/mL or $> 100,000$ copies/mL).

Mean \pm 95% CI and median (Q1, Q3) of the change from baseline in \log_{10} HIV-1 RNA and CD4+ cell counts will be plotted by visit.

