$$\begin{aligned} \text{Adherence(\%)} &= 100 \times \frac{\text{Total No. of pills taken}}{\text{Total No. of pills prescribed}} \\ &= 100 \times \frac{\sum \sum \text{No. of pills taken at each dispensing period for each drug}^{[1]}}{\sum \sum \text{No. of pills prescribed at each dispensing period for each drug}^{[2]}} \end{aligned}$$

13) Efficacy Analysis

- a) For categorical efficacy response (eg, Subjects with HIV-1 RNA < 50 copies/mL as determined by US FDA-defined snapshot algorithm, M=F, or M=E Analyses): the proportion difference between LEN-containing regimen groups (Treatment Groups 1 to 3) and the B/F/TAF group (Treatment Group 4) and its 95% CIs are calculated based on the MH proportion adjusted by baseline HIV-1 RNA stratum ($\leq 100,000$ vs. $> 100,000$ copies/mL) (see SAP Section 6.2 and 6.3 for details). The following SAS code will be used to compute p-value, where *brnac* is the baseline HIV-1 RNA stratum, *trtgrp* is the treatment, and *response* is the categorical efficacy response.

```
proc freq data=adeff;  
  tables brnac*trtgrp*response/cmh; /*p value from general  
  association*/  
run;
```

- b) All the ANOVA model for continuous efficacy variable (eg, CD4+): The differences in changes from baseline in \log_{10} HIV-1 RNA and CD4+ cell count between treatment groups and the associated 95% CI will be constructed using an ANOVA, including baseline HIV-1 RNA stratum *brnac*, region stratum *region*, and treatment *trtgrp* as fixed effects in the model.

```
proc glm data=adeff;  
  class brnac region trtgrp;  
  model CD4=brnac region trtgrp;  
  lsmeans trtgrp /alpha=0.05 cl pdiff;  
run;
```

14) Listing for US FDA-defined snapshot outcome:

In addition flag the values of HIV-1 RNA < 50 or ≥ 50 copies/mL for virologic outcomes.

Flag the last available HIV-1 RNA value while on treatment for the following categories:

- a) HIV-1 RNA ≥ 50 copies/mL - Discontinued Study Drug Due to Other Reasons and Last Available HIV-1 RNA ≥ 50 copies/mL
- b) No virologic Data - Discontinued Study Drug Due to Other Reasons and Last Available HIV-1 RNA < 50 copies/mL

15) Injection site reaction (ISR)

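### The CD4 change comparisons leave out baseline CD4 count: the estimates stay valid, but they give up some precision and carry part of any chance imbalance against 25 controls

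*SAP*

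**What the plan says.** Protocol 8.5.2 and SAP 6.2.1 compare CD4 change between arms by a model "constructed using analysis of variance (ANOVA) models adjusting for the baseline HIV-1 RNA level", meaning the two-level class split at 100,000 copies/mL. SAP 6.2.1 adds p-values to the 95% intervals and names each of Groups 1 to 3 against Group 4. The code in SAP Appendix 3 item 13b is "model CD4=brnac region trtgrp". Its lead-in gives change from baseline as the outcome, so I read the variable CD4 as the change. The code includes a region term found neither in SAP 6.2.1 and 3.3 nor in the protocol text.

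None of the three places has baseline CD4 as a covariate. It is available: the procedures table schedules CD4 at Screening and at Day 1 before dosing, SAP 3.8.1 states that "Baseline Value is defined as the last value obtained on or prior to the first dose of study drug", and SAP 5.2 tabulates it by arm. On design, SAP 3.3 says "Randomization was stratified by HIV-1 RNA level", so nothing balances CD4 across arms. Planned sizes are "Treatment Groups 1 to 3, n = 50" against 25 on B/F/TAF.

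**The concern.** Change scores usually correlate with their own baseline, often negatively, because an arm that starts low by chance tends to gain more. A model that adjusts for viral-load class but not for the outcome's own starting value leaves that variation in the residual. It also lets part of a chance imbalance into the contrast. With 25 controls such imbalances can be sizeable, and all three contrasts share those controls, so a control arm that starts high or low pushes all three the same way.

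The programme has met a related problem. Protocol 1.2.2.7 describes post hoc analyses in another study (24 v 12) prompted by unequal baseline CD4, though that endpoint was virologic. At stake here are the precision and reading of a descriptive secondary endpoint. The primary endpoint is not touched.

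**Working it through.** **The plan's own figure.** The only power stated is 39% for the binary primary endpoint. It reproduces: SE = sqrt(0.909 × 0.091 × (1/50 + 1/25)) = 0.0704, and Φ(0.12/0.0704 − 1.96) = 39.9%. It does not bear on CD4, for which no SD, power or precision is given.

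**Inputs.**
- Baseline CD4 Q1 to Q3 of 332 to 599 (Protocol 1.2.2.8). Assuming normality, SD = (599 − 332)/1.349 = 198.
- Week 54 CD4 change of 213 (182.1) for all lenacapavir and 193 (191.1) for B/F/TAF (same section). I read the brackets as SDs and use 187, about midway.
- Correlation r of change with baseline: not in the documents. Assumed range 0 to −0.5.

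**Chance imbalance.** SE = 198 × sqrt(1/52 + 1/25) = 48.2 cells at the sizes dosed, or 48.5 for the planned 50 v 25. The 95% range is about ±95 cells.

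**Unadjusted contrast.** For 50 v 25, SE = 187 × sqrt(1/50 + 1/25) = 45.8 cells; 95% half-width 1.96 × 45.8 = 89.8.

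**What passes through.** The slope of change on baseline is b = r × 187/198, and the shift is b times the imbalance. At a 1-SE imbalance this reduces to r × 45.8. With the covariate, the SE is multiplied by sqrt(1 − r²).

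| r | slope b | shift at 1 SE (cells, absolute) | shift at 1.96 SE | half-width with covariate | narrower by |
|---|---|---|---|---|---|
| 0 | 0 | 0 | 0 | 89.8 | 0% |
| −0.1 | −0.09 | 4.6 | 9.0 | 89.3 | 0.5% |
| −0.2 | −0.19 | 9.2 | 18.0 | 88.0 | 2.0% |
| −0.3 | −0.28 | 13.7 | 26.9 | 85.6 | 4.6% |
| −0.4 | −0.38 | 18.3 | 35.9 | 82.3 | 8.3% |
| −0.5 | −0.47 | 22.9 | 44.9 | 77.8 | 13.4% |

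**One anchored case.** If CD4 spread at Week 54 equals that at baseline and the SD of change is 182.1, the baseline-to-Week 54 correlation is 1 − 182.1²/(2 × 197.9²) = 0.58 and the slope is 0.58 − 1 = −0.42. A 1-SE imbalance then shifts the contrast by 0.42 × 48.2, about 20 cells. Here r = −0.42 × 197.9/182.1 = −0.46, inside the table's range.

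**Validity of the planned model.** In 20,000 simulated trials at each of r = −0.2, −0.3 and −0.5 (50 v 25), the unadjusted estimate had mean error within 0.13 cells and type I error of 4.9% to 5.2%. Its SD against that of the adjusted estimate was 46.1 v 45.5, 45.7 v 43.8 and 46.1 v 40.2.

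**Comparison with the planned contrasts.** At Week 54: 206 − 193 = +13, 212 − 193 = +19 and 220 − 193 = +27 cells for Groups 1, 2 and 3.

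**The case against.** The strongest reply is that the planned analysis is sound and little is gained. The outcome is a change score, so baseline is already subtracted. Randomisation keeps the estimate unbiased on average, and the test holds its level. Sampling error, with a half-width near 90 cells, dwarfs any likely shift, so the sign of a 13- to 27-cell difference is unresolved with or without the covariate. SAP 5.2 tabulates and compares baseline CD4 across arms, so an imbalance would be visible, and Protocol 1.2.2.8 reports the arms as alike on baseline disease characteristics. SAP 3 calls the tests descriptive, and SAP 3.5 calls the trial non-confirmatory.

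The mechanism may also be weak. With the SDs above, the slope is zero when the baseline-to-Week 54 correlation is 1/sqrt(1 + (182.1/197.9)²) = 0.74, and positive beyond that.

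All of this stands and limits the weight of the point. None of it shows that the covariate would do harm. Tabulating an imbalance does not remove it, and no by-arm CD4 values are given against which to check the statement of similarity. Under a positive slope the shift changes sign, and the covariate still removes it.

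**Conclusion.** The omission is real and in all three places. Its cost is modest: some loss of precision, and a shift conditional on the observed imbalance. For r between 0 and −0.5, a 1-SE imbalance shifts a contrast by 0 to about 23 cells and the covariate narrows the interval by 0 to 13%. This rests on a baseline SD inferred from quartiles, bracketed figures read as SDs, and an assumed r.

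Stronger readings are tempting but not supported:
- A reader might infer that an imbalance enters the estimate in full, or that the analysis is biased. Only the slope fraction enters, and the average bias is nil.
- A reader might assume a baseline-to-Week 54 correlation of 0.5 and reach a 29-cell shift and a 42% cut in residual variance. With SD of change 182.1, that needs the Week 54 SD to fall to about 160 while mean CD4 rises by about 200, which nothing in the documents suggests.
- A reader might set 213 against 193. That is the pooled lenacapavir figure; SAP 6.2.1 plans each group separately.

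This is a free improvement to a secondary analysis, with no bearing on the primary result.

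**What to change.** In Protocol 8.5.2, SAP 6.2.1 and the SAP Appendix 3 item 13b code, analyse CD4 change by ANCOVA with treatment, baseline HIV-1 RNA stratum and continuous baseline CD4 count. At the same time reconcile the code's region term with the text: either justify it in SAP 3.3 and 6.2.1 or remove it, since SAP 6.5 declares no departure from the protocol's efficacy analyses.

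Timing matters. Protocol 1.2.2.8 already reports CD4 change at Weeks 28, 38 and 54, so replacing the model for those visits would be a change made after seeing results. Prespecify the ANCOVA for Week 80. For the visits already reported, keep the planned ANOVA and show the ANCOVA beside it as a labelled sensitivity analysis.

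The cost is one term, one degree of freedom and a short text amendment. No new data are needed.

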6.3. Other Efficacy Endpoints

6.3.1. Proportion of Subjects with HIV-1 RNA < 50 copies/mL by Missing = Failure and Missing = Excluded Analyses

Number and percentage of subjects with HIV-1 RNA < 50 copies/mL by visit will be analyzed using the following 2 analyses:

- Missing = Failure (M = F):

In this approach, missing data will be treated as virologic failure and summarized into the “missing” category (see list of HIV-RNA categories below). Results will be summarized by treatment group for all visits up to Week 54.

- Missing = Excluded (M = E):

In this approach, missing data will be excluded in the computation of the percentages (ie, missing data points will be excluded from both the numerator and denominator in the computation). The denominator for percentages at a visit is the number of subjects in the FAS with nonmissing HIV-1 RNA value at that visit. Results will be summarized by treatment group for all visits up to Week 54.

For both M = F and M = E analyses, the number and percentage of subjects with HIV-1 RNA in the following categories will be summarized based on the FAS:

- < 50 copies/mL
 - < 20 copies/mL
 - < 20 copies/mL Not Detectable
 - < 20 copies/mL Detectable
 - 20 to < 50 copies/mL
- 50 to < 200 copies/mL
- 200 to < 400 copies/mL
- 400 to < 1000 copies/mL
- \geq 1000 copies/mL
- Missing (only applicable to M = F analysis)

Statistical comparison between each of the LEN-containing treatment groups (Treatment Groups 1-3) and the B/F/TAF group (Treatment Group 4) will be performed. Point estimates and its 95% CIs will be estimated using stratum-adjusted MH proportion as described in Section 6.1.2. The associated p-values will be estimated based on the CMH test stratified by baseline HIV-1 RNA level (\leq 100,000 copies/mL or $>$ 100,000 copies/mL).

6.4. Subgroup Analysis

Subgroups defined in Section 3.4.1 will be performed for the proportion of subjects with HIV-1 RNA < 50 copies/mL at Week 54 as determined by the US FDA-defined snapshot algorithm. Subgroup analysis will be performed on subjects who have reached Week 54 at the time for the Week 54 analysis in the FAS for on-treatment data. Results will be descriptive and the associated 95% CIs will be constructed using Exact method.

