6.3.3. Treatment Assessments (Week 4 – Week 28)

The following evaluations are to be completed at Week 4 and every 6 weeks until Week 28, unless otherwise specified.

All study visits are to be completed within ± 2 days of the protocol-specified visit date (based on the Day 1 visit), unless otherwise specified.

Regularly scheduled evaluations will be made on all participants whether or not they continue to receive their study regimen.

- Prior to completion of other study procedures, participants will read the questionnaires by themselves and provide answers directly onto the questionnaires (if available) (**Week 4, Week 28**)
 - HIV Treatment Satisfaction Questionnaire status (HIVTSQ12s), HIVDQoL, and EQ-ED-5L
- Review of AEs and changes in concomitant medications
- Complete physical examination (**Week 28**) (urogenital/anorectal exams will be performed at the discretion of the Investigator) or symptom-directed physical examination, as needed
- Vital signs (blood pressure, pulse, respiration rate, and temperature), including weight
- Obtain blood and urine samples as described in Section 6.5
- Document bottle dispensation for study drug(s) for all visits
 - Participants randomized to Treatment Groups 1 and 2 will be dispensed F/TAF (200/25 mg) (**Week 4, Week 10, Week 16, Week 22**)
 - Participants in Treatment Group 1 will discontinue F/TAF and will be dispensed TAF (25 mg) (**Week 28**)
 - Participants in Treatment Group 2 will discontinue F/TAF and will be dispensed BIC (75 mg) (**Week 28**)
 - Participants randomized to Treatment Group 3 will be dispensed GS-6207 (50 mg) and F/TAF (200/25 mg)
 - Participant randomized to Treatment Group 4 will be dispensed B/F/TAF (50/200/25 mg)

- Document accountability for study drug(s) for all visit
- GS-6207 SC injection for Treatment Group 1 and 2 participants only (**Week 28**)
 - Provide Injection Site Reaction Assessment Worksheet and instruct the participants to measure and report injection site reactions following the administration of the SC injections
- Participants who meet the criteria for virologic failure will be managed according to the Management of Virologic Rebound Section 6.7

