2.2. Primary Analysis

The Week 54 interim analysis is a planned primary analysis and will be conducted after all subjects have completed Week 54 visit or have prematurely discontinued the study drug, outstanding data queries have been resolved or adjudicated as unresolvable, and the data have been cleaned and finalized for the analysis.

This SAP describes the analysis plan for the Week 54 interim analysis, the primary analysis of this study.

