3.4. Examination of Subject Subgroups

3.4.1. Subject Subgroups for Efficacy Analyses

The proportion of subjects with HIV-1 RNA < 50 copies/mL at Week 54 as determined by the United States (US) Food and Drug Administration (FDA)-defined snapshot algorithm {[U. S. Department of Health and Human Services 2015](#)} will be analyzed for the following subject subgroups based on FAS:

- Age (years): (a) < 50 and (b) ≥ 50
- Sex: (a) male and (b) female
- Race: (a) black and (b) nonblack
- Baseline HIV-1 RNA (copies/mL): (a) $\leq 100,000$ and (b) $> 100,000$
- Baseline CD4 Cell Count (/uL): (a) < 200 and (b) ≥ 200

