6.1.1. US FDA-defined Snapshot Algorithm

The analysis window at Week 54 is defined as from Study Day 323 to Study Day 413, inclusive. All HIV-1 RNA data collected on-treatment (ie, data collected up to 1 day after the last dose date) will be used in the US FDA-defined snapshot algorithm. Virologic outcome will be defined as the following categories:

- HIV-1 RNA < 50 copies/mL: this includes subjects who have the last available on-treatment HIV-1 RNA < 50 copies/mL in the Week 54 analysis window
- HIV-1 RNA \geq 50 copies/mL: this includes subjects
 - Who have the last available on-treatment HIV-1 RNA \geq 50 copies/mL in the Week 54 analysis window, or
 - Who do not have on-treatment HIV-1 RNA data in the Week 54 analysis window and
 - Who discontinue study drug prior to or in the Week 54 analysis window due to lack of efficacy, or
 - Who discontinue study drug prior to or in the Week 54 analysis window due to reasons other than AE, death, or lack of efficacy and have the last available on-treatment HIV-1 RNA \geq 50 copies/mL
- No Virologic Data in the Week 54 analysis window: this includes subjects who do not have on-treatment HIV-1 RNA data in the Week 54 analysis window because of the following:
 - Discontinuation of study drug prior to or in the Week 54 analysis window due to AE or death (regardless of whether the last available on-treatment HIV-1 RNA < 50 copies/mL or not) or,
 - Discontinuation of study drug prior to or in the Week 54 analysis window due to reasons other than AE, death, or lack of efficacy and the last available on-treatment HIV-1 RNA < 50 copies/mL or,
 - Missing data during the window but on study drug.

The flowchart of the US FDA-defined snapshot algorithm is provided in Section 12 ([Appendix 2](#)).

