6.1.2. Primary Analysis of the Primary Efficacy Endpoint

The proportion of subjects with HIV-1 RNA < 50 copies/mL as determined by the US FDA-defined snapshot algorithm at Week 54 will be based on the FAS. Point estimates ($P_1 - P_2$) and its 95% confidence interval (CI) for the difference in the response rates between each of the LEN-containing regimen groups (Treatment Groups 1 to 3) and the B/F/TAF group (Treatment Group 4) will be constructed using stratum-adjusted Mantel-Haenszel (MH) proportion as described as follows {Koch 1989}, stratified by baseline HIV-1 RNA level ($\leq 100,000$ copies/mL or $> 100,000$ copies/mL):

$$P_1 - P_2 \pm Z_{(1-\alpha/2)} * SE(P_1 - P_2),$$

where

- $(P_1 - P_2) = \frac{\sum w_h d_h}{\sum w_h}$, is the stratum-adjusted MH proportion difference,

where $d_h = p_{1h} - p_{2h}$ is the difference in the response rate between of the LEN-containing regimen groups (Treatment Groups 1 to 3) and the B/F/TAF group (Treatment Group 4) in stratum h ($h=1$ to 4).

- $w_h = \frac{n_{1h} n_{2h}}{n_{1h} + n_{2h}}$, is the weight based on the harmonic mean of sample size per treatment group for each stratum where n_{1h} and n_{2h} are the sample sizes of the LEN-containing regimen groups (Treatment Groups 1 to 3) and the B/F/TAF group (Treatment Group 4) in stratum h .

- $SE(P_1 - P_2) = \sqrt{\frac{\sum w_h^2 \left[\frac{p_{1h}^* (1 - p_{1h}^*)}{n_{1h} - 1} + \frac{p_{2h}^* (1 - p_{2h}^*)}{n_{2h} - 1} \right]}{(\sum w_h)^2}}$, where $p_{1h}^* = \frac{m_{1h} + 0.5}{n_{1h} + 1}$ and

$p_{2h}^* = \frac{m_{2h} + 0.5}{n_{2h} + 1}$. m_{1h} and m_{2h} are the number of subjects with HIV-1 RNA < 50 copies/mL in the LEN-containing regimen groups (Treatment Groups 1 to 3) and the B/F/TAF group (Treatment Group 4) in stratum h .

- $\alpha = 0.05$ for this study
- $Z_{(1-\alpha/2)} = Z_{0.9750} = 1.96$ is the 97.50th percentile of the normal distribution

Note that if the computed lower confidence bound is less than -1 , the lower bound is defined as -1 . If the computed upper confidence bound is greater than 1 , the upper bound is defined as 1 .

The number and percentage of subjects with HIV-1 RNA < 50 copies/mL at Week 54 will be summarized. The associated p-values will be estimated based on the CMH test stratified by baseline HIV-1 RNA level ($\leq 100,000$ copies/mL or $> 100,000$ copies/mL).

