6.2. Secondary Efficacy Endpoints

The secondary efficacy endpoints of this study are:

- The proportion of subjects with HIV-1 RNA < 50 copies/mL at Weeks 28, 38, and 80 as determined by the US FDA-defined snapshot algorithm
- The change from baseline in \log_{10} HIV-1 RNA and in CD4+ cell count at Weeks 28, 38, 54, and 80

The proportion of subjects with HIV-1 RNA < 50 copies/mL at Week 28 as determined by the US FDA-defined snapshot algorithm has been performed in the Week 28 analyses and will not be repeated here. The proportion of subjects with HIV-1 RNA < 50 copies/mL at Week 38 as determined by the US FDA-defined snapshot algorithm will be analyzed using the same method as the primary analysis for the primary endpoint based on the FAS.

The proportion of subjects with HIV-1 RNA < 50 copies/mL as determined by the US FDA-defined snapshot algorithm at Week 80 will not be summarized for the Week 54 interim analysis as the majority of subjects will not have reached the timepoints of interest.

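### Does the wording of SAP 6.4 cut the Week 54 subgroup tables to less than the Full Analysis Set?

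*SAP*

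**What the plan says.** Two sections of the SAP describe the population for one set of tables. Section 3.4.1 says that the Week 54 snapshot proportion "will be analyzed for the following subject subgroups based on FAS". The FAS (SAP 3.1.2) requires only randomization and one dose. Section 6.4 refers back to 3.4.1 for the subgroups and names the snapshot outcome as the endpoint, then says the analysis will be "performed on subjects who have reached Week 54 at the time for the Week 54 analysis in the FAS for on-treatment data". It adds that the results are descriptive, with exact 95% intervals.

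The overall primary analysis carries no such condition: the proportion "as determined by the US FDA-defined snapshot algorithm at Week 54 will be based on the FAS" (SAP 6.1.2). SAP 2.2 sets the timing: the analysis "will be conducted after all subjects have completed Week 54 visit or have prematurely discontinued the study drug".

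**The concern.** Read side by side, 6.4 is narrower than 3.4.1, and its key phrase is undefined. A programmer could take it in three ways: enough time has passed since Day 1; the participant is still in the study; or the participant is still on drug at Week 54. The closing reference to on-treatment data could push a reader to the third.

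That reading would matter. The snapshot keeps participants who stop drug early in the denominator, as non-responders if they have no on-treatment value in the window. Removing them would make the subgroup tables answer a different question from the primary table. The subgroup levels would also fail to add up to the arm totals, so a reader could not reconcile the two.

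**Working it through.** **What the words can mean**

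- *On-treatment* is defined. SAP 6.1.1 uses it for HIV-1 RNA "data collected up to 1 day after the last dose date", and the footnote to SAP Appendix 2 agrees. Both are rules about which values count, not which participants count. In 6.4 the term therefore most simply restates the snapshot's own data rule.
- *Reached* appears in the same sense in SAP 6.2, where Week 80 results are deferred "as the majority of subjects will not have reached the timepoints of interest". That is elapsed time.
- *In the FAS*, together with the snapshot endpoint, conflicts with an on-drug filter. The algorithm has explicit categories for people who stop drug before the window, and such a filter would empty them.
- The still-in-study reading would keep anyone who stops drug but goes on attending. The protocol expects this: "Regularly scheduled evaluations will be made on all participants whether or not they continue to receive their study regimen" (Protocol 6.3.3, Weeks 4 to 28), and Section 6.4.1 asks most who stop before Week 80 to keep attending through that visit.

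**Elapsed-time reading: what is left to exclude**

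The trigger in SAP 2.2 is met once every participant has completed Week 54 or stopped drug. Someone still on drug has therefore reached Week 54. The condition can exclude only a participant who stopped drug and whose Week 54 date falls after the data cut. The cut cannot precede the Week 54 visit of the last participant still on drug, so this person must have started at about the same time as, or after, that participant.

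Size, from the results in Protocol 1.2.2.8:

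- Responders on lenacapavir: 47 + 45 + 44 = 136. Denominator: 52 + 53 + 52 = 157. Rate 136/157 = 86.6%, as the protocol reports (exact 95% CI 80.3 to 91.5).
- Drop one non-responder: 136/156 = 87.2%, a rise of 0.6 points.
- The same within the oral group: 44/52 = 84.6% becomes 44/51 = 86.3%, a rise of 1.7 points.

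**On-drug reading: no single size or direction**

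The result depends on a cut-off that the SAP does not give. Inputs from Protocol 1.2.2.8:

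| | Stopped drug by the cut | Week 54 non-responders |
|---|---|---|
| SC lenacapavir | 17 of 105 | 5 + 8 = 13 |
| Oral lenacapavir | 4 of 52 | 52 − 44 = 8 |
| B/F/TAF | 1 of 25 | 25 − 23 = 2 |

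1. *Cut-off at the opening of the window.* SAP 6.1.1 states: "The analysis window at Week 54 is defined as from Study Day 323 to Study Day 413, inclusive". Values count to one day after the last dose, so a last dose before Day 322 leaves no usable value and means non-response. At most min(17, 13) + min(4, 8) = 17 lenacapavir non-responders could go, giving 136/140 = 97.1%. For the oral group, 44/48 = 91.7%. For B/F/TAF, 23/24 = 95.8%.
2. *Cut-off at nominal Week 54, Day 378 (SAP Table 3-1).* Responders who stopped between Day 322 and Day 377 would go too. If all 4 oral participants who stopped drug were such responders, the rate would fall: 40/48 = 83.3%.
3. *An on-treatment value required in the window.* Participants on drug with a missing value would also go. At least 8 − 4 = 4 oral non-responders had not stopped drug, and the documents do not say how many of them had missing data. The 91.7% in item 1 is then not a bound.

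Using at least 54 weeks of exposure as a proxy (140 of 157, Protocol 1.2.2.8), the pooled lenacapavir rate could lie anywhere from (136 − 17)/140 = 119/140 = 85.0% to 136/140 = 97.1%. The proxy is rough, because SAP 3.8.1 runs exposure to the last study date for those who received an injection and then stopped drug.

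**The case for a change.** The strongest case for a change is that the condition does no useful work on any reading, contradicts 3.4.1 on its face, and could be removed with one sentence. The elapsed-time reading is not strictly harmless, since it could drop a participant whom the primary analysis keeps. Some rows are small as well: 182 − 155 = 27 participants had baseline HIV-1 RNA above 100,000 copies/mL, so losing one or two would show. SAP 6.5 declares no change from the protocol's efficacy analyses, but this does not settle the matter, because Protocol 8.5 specifies no subgroup analyses.

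All of that stands as a comment on drafting. It does not show that the plan, followed on its natural reading, gives misleading tables. The large movements all require the reading that conflicts with the rest of 6.4, and even there the direction is not fixed. Nothing in the documents indicates that the on-drug version was programmed. The SAP was signed in October 2021 and the protocol already reports Week 54 results, so rewording the SAP would no longer guide anyone.

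**Conclusion.** This is loose wording that analysts can resolve sensibly from the rest of the SAP, and no change to the plan follows. Section 3.4.1 gives the population, 6.1.1 the outcome and the on-treatment rule, and 2.2 makes the extra condition nearly redundant. On the elapsed-time reading the effect is none, or a participant or so among the last enrolled, at 0.6 points each in the pooled lenacapavir rate if a non-responder.

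The conclusion rests on two assumptions: that the phrase was applied as elapsed time, and that few if any participants stopped drug early with a Week 54 date after the cut. The documents confirm neither. The published tables would reveal a departure: within each subgroup factor the levels should add up to 52, 53, 52 and 25, less any participant missing that factor. The subgroup results are descriptive, SAP 3.5 calls the trial non-confirmatory, and the primary estimate and its interval do not depend on this sentence.
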